# Appendix 2. ACR Classification for OA of the Knee

Using history, physical examination, and radiographic findings:

# Pain in the knee

And 1 of the following:

- Over 50 years of age
- Less than 30 minutes of morning stiffness
- Crepitus on active motion and osteophytes

(Altman, et al., 1986)

# Appendix 3. Kellgren and Lawrence System for Classification of OA of the Knee

- Grade 0: No radiographic features of OA are present
- Grade 1: Doubtful joint space narrowing (JSN) and possible osteophytic lipping
- Grade 2: Definite osteophytes and possible JSN on anteroposterior weight-bearing radiograph
- Grade 3: Multiple osteophytes, definite JSN, sclerosis, possible bony deformity
- Grade 4: Large osteophytes, marked JSN, severe sclerosis and definite bony deformity

(Kellgren & Lawrence, 1957)

This document describes the rules and conventions to be used in the presentation and analysis of safety, tolerability, pharmacokinetics (PK), and pharmacodynamics (PD) data for Protocol CBR-KA34-3001. It describes the data to be summarized and analyzed, including specifics of the statistical analyses to be performed.

This statistical analysis plan (SAP) is based on protocol Amendment 4, dated 02 April 2020.

2. STUDY OBJECTIVES

2.1. **PRIMARY OBJECTIVE**

To assess the safety and tolerability of KA34 when administered via intra-articular injection to the knee joint

2.1.1. **PRIMARY ENDPOINTS**

Incidence, relatedness, severity, and duration of treatment emergent adverse events (TEAEs)

2.2. **SECONDARY OBJECTIVES**

- To identify any dose limiting toxicity and determine the maximum tolerated dose of KA34
- To determine pharmacokinetic properties of KA34 in plasma

2.2.1. **SECONDARY ENDPOINTS**

- Changes from baseline in clinical laboratory test results, vital signs, or electrocardiogram (ECG) results
- Clinically significant findings on physical examination
- Pharmacokinetic parameters of KA34 in plasma including:
 - Maximum observed plasma concentration (C_{max})
 - Dose-adjusted C_{max} (C_{max}/dose)
 - Time to maximum observed plasma concentration (T_{max})

Document: CALIBR CBR-KA34-3001 SAP Final 1.0 Author: Version Number: Final 1.0 PPD Version Date: 15MAY2020 Template No: CC

Effective Date: 01Apr2016

- Area under the plasma concentration vs. time curve from time zero to the last quantifiable concentration (AUC_{0-t})
- Dose-adjusted AUC_{0-t} (AUC_{0-t}/dose)
- AUC from time zero to infinity (AUC_{0-inf})
- Dose-adjusted AUC_{0-inf} (AUC_{0-inf} /dose)
- Terminal elimination rate constant (λz)
- Terminal half-life (t_{1/2})
- Apparent clearance (CL/F)
- Volume of distribution (Vz/F)

2.3. **EXPLORATORY OBJECTIVES**

- To assess changes in cartilage and osteoarthritis (OA) symptoms after administration of KA34
- To collect and bank biospecimen samples for exploratory biomarker research

2.3.1. **EXPLORATORY ENDPOINTS**

- Serum levels of the N-propeptide of type IIA collagen (PIIANP) as a pharmacodynamic marker of collagen synthesis
- Urinary excretion of C-terminal cross-linking telopeptide of type II collagen (CTX-II) as a pharmacodynamic marker of collagen degradation
- Change from baseline in Whole-Organ Magnetic Resonance Imaging Score (WORMS) of the index knee
- Change from baseline of the Western Ontario and McMaster Universities Osteoarthritis Index (WOMAC) Version 3.1 total score and the WOMAC pain and function subscale scores
- Utilize banked biospecimen samples for exploratory research related to drug response in OA

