6.4. Reference Start Date and Study Day

Study Day will be calculated from the reference start date, and will be used to show start/stop day of assessments and events.

Reference start date is defined as the day of the first dose of study medication, (Day 1 is the day of the first dose of study medication), and will appear in every listing where an assessment date or event date appears.

• If the date of the event is on or after the reference date then: Study Day = (date of event – reference date) + 1.

Document: CALIBR_CBR-KA34-3001_SAP_Final 1.0
Author: PPD Version Number: Final 1.0
Version Date: 15MAY2020

Template No: CE Reference: CE

Copyright © 2017 IQVIA. All Rights Reserved.

• If the date of the event is prior to the reference date then: Study Day = (date of event – reference date).

In the situation where the event date is partial or missing, Study Day, and any corresponding durations will appear partial or missing in the listings.

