17.1. ADVERSE EVENTS

Adverse Events (AEs) will be coded using MedDRA central coding dictionary, Version 21.0.

Treatment emergent adverse events (TEAEs) are defined as AEs that started on or after the first dose of study medication.

Pretreatment AEs are defined as AEs occurring prior to dosing. These events will be presented in the listings only and are not included in the tabular summary of AEs.

See APPENDIX 2 for handling of partial dates for AEs. In the rare case where it is not possible to assess treatment emergence, the AE will be classified as treatment emergent (i.e. the worst case).

Severity

AE Severity is classified as mild/moderate/severe. If a subject reports a TEAE more than once within that SOC/ PT, the AE with the worst case severity will be used in the corresponding severity summaries.

Relationship to Study Medication

Relationship to study medication, as indicated by the Investigator, is classified as "not related", "unlikely related", "possibly related", or "related". A "related" TEAE is defined as a TEAE with a relationship to study medication as "possibly related" or "related" to study medication. TEAEs with a missing relationship to study medication will be regarded as "related" to study medication. If a subject reports the same AE more than once within that SOC/ PT, the AE with the worst case relationship to study medication will be used in the corresponding relationship summaries.

All AE tabulations will be performed for the SAD and MAD study part by dose levels and for all active treated subjects overall, and will include the number and percentage of subjects. Incidence of TEAEs will be tabulated by the following:

- Overall summary for TEAEs displaying number (percent) of subjects with at least one TEAE, with at least one related TEAE, with at least one severe TEAE, with at least one severe related TEAE, with at least one serious AE, with TEAEs leading to discontinuation and with TEAEs leading to death
- Summary of TEAEs by SOC and PT
- Summary of Treatment-related AEs by SOC and PT
- Summary of TEAEs by SOC, PT and Severity
- Summary of Treatment-related AEs by SOC, PT and Severity
- Summary of Serious TEAEs by SOC, PT and Severity

Document: CALIBR_CBR-KA34-3001_SAP_Final 1.0
Author: PPD Version Number: Final 1.0
Version Date: 15MAY2020

Template No: C Reference: Reference: C

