17.1.3. CTC GRADING FOR ADVERSE EVENTS

AEs will be graded by the clinics using the Common Terminology Criteria for Adverse Events (CTCAE) version 5 grading system. A summary table will be presented for TEAEs with CTCAE grade >=3 by SOC and PT.

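### Duration is one of four components of the primary endpoint, but the SAP body neither derives TEAE duration nor summarises it in any of its seven planned AE tables

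*SAP*

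**What the plan says.** Protocol 2.2 and SAP 2.1.1 give the same primary endpoint: "Incidence, relatedness, severity, and duration of treatment emergent adverse events (TEAEs".

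SAP 17.1 describes the AE tabulations. They are produced by dose level and "for all active treated subjects overall, and will include the number and percentage of subjects". Six tables follow. The first is the "Overall summary for TEAEs displaying number (percent) of subjects with at least one TEAE", with further lines for related, severe, severe related and serious events and for events leading to discontinuation or death. The others include "Summary of Treatment-related AEs by SOC and PT" and "Summary of TEAEs by SOC, PT and Severity". SAP 17.1.3 adds a seventh: "A summary table will be presented for TEAEs with CTCAE grade >=3 by SOC and PT".

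Outside the endpoint definition, the only reference to how long an event lasts is in SAP 6.4. It says that when an event date is partial or missing, the study day and "any corresponding durations will appear partial or missing in the listings".

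SAP 3.3 states that the analysis does not differ meaningfully from the protocol. Protocol 9.5 promises standard summary statistics for TEAEs.

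**The concern.** A component named in the primary endpoint should have a defined derivation and at least one planned summary. Duration has neither in the SAP body.

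Duration carries information here that the other three components do not:

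- Protocol 5.4 describes post-injection flare by its time course, says that it usually resolves within 48 hours, and requires every instance to be reported as an AE. Duration therefore helps to separate the expected local reaction from a persistent one.
- Severity is not a stand-in. Protocol 8.3 grades the maximum interference with usual function, not how long it lasts.
- In the multiple-dose part, subjects receive four weekly injections. SAP 17.1 reduces repeated events within a system organ class and preferred term to the worst severity or worst relationship. Four brief reactions and one reaction that persists across injections could give the same entry in the subject counts, if coded and graded alike.

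What is at stake is whether the dose groups can be compared on duration from a prespecified summary, rather than by reading listings after unblinding.

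**Working it through.** No power, alpha or event-rate figure bears on this point, and the plan states no figure to reproduce. The check is a cross-tabulation of the four endpoint components against each AE table in the SAP body, followed by a search for any derivation.

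**Step 1. Coverage of the components.**

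| Planned table | Incidence | Relatedness | Severity | Duration |
|---|---|---|---|---|
| Overall TEAE summary (17.1) | yes | yes | yes | no |
| TEAEs by SOC, PT (17.1) | yes | no | no | no |
| Related AEs by SOC, PT (17.1) | yes | yes | no | no |
| TEAEs by SOC, PT, severity (17.1) | yes | no | yes | no |
| Related AEs by SOC, PT, severity (17.1) | yes | yes | yes | no |
| Serious TEAEs by SOC, PT, severity (17.1) | yes | no | yes | no |
| CTCAE grade 3 or higher by SOC, PT (17.1.3) | yes | no | yes | no |
| **Total of 7** | **7** | **3** | **5** | **0** |

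Three of the four components have at least one planned summary. Duration has none.

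**Step 2. Derivation.** SAP 6.7 (Common Calculations) defines change and percent change from baseline only. SAP 6.4 defines study day and uses it to show the start and stop day of events, so the dates needed for a duration appear to be collected. No section of the SAP body gives a start/stop convention, a unit, or a treatment of events still ongoing at last contact. Such events are foreseeable, since protocol 8.1 provides follow-up for AEs that are ongoing when AE collection ends. SAP 7.1 does not impute missing safety data, so an event without a stop date has no computable duration. If such events were silently dropped, a summary would lose the events still unresolved at last contact and would tend to look too short.

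**Step 3. Is it a declared choice?** Protocol section 9 lets the SAP modify the outlined analyses, but requires major modifications of the primary endpoint definitions or their analyses to be reflected in a protocol amendment as well. SAP 3.3 declares no meaningful change. Nothing says that duration is to be listed only.

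**Step 4. What a summary could support.** From SAP 3.1, the active group sizes are 3, 3, 6 and 6 (single dose) and 9, 9 and 9 (multiple dose). Placebo numbers are 1 + 1 + 2 + 2 = 6 and 3 + 3 + 3 = 9. SAP 6.1 prints N/A when fewer than 2 values are available in a group. A grid by preferred term and dose level would be largely N/A. Rows for all TEAEs and for related TEAEs would hold more.

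**Step 5. Unit.** With stop date minus start date plus 1, a reaction of a few hours that crosses midnight scores 1 + 1 = 2 days, and one of exactly 48 hours scores 2 + 1 = 3 days. Whole days are too coarse against a 48-hour description, so hours are preferable where times are recorded. The documents do not say whether AE times are recorded.

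**The case against.** The strongest case on the other side has four parts.

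1. **Listings are a planned form of reporting.** A reader might infer that duration will go unreported. The documents do not support that: SAP 6.4 implies that durations appear in by-subject listings, where an event lasting weeks would show by its start and stop days. This stands, and it limits the point to the absence of a derivation and a summary. With groups of 3 to 9 active subjects, listings are also a reasonable place for event-level detail.
2. **The tables are not confined to subject counts.** A reader might take section 17.1 to exclude any other statistic. It says the tabulations are by dose level "and will include the number and percentage of subjects", which does not rule out more. This stands too, but event counts would not give duration either.
3. **Some text was not available.** SAP section 8 says the shells supplied with it set the format and content of the outputs, and Appendix 2 is titled for partial-date conventions. The shells and the appendix text were not available, so a duration output or rule there cannot be excluded. Nothing in the SAP body calls for one.
4. **The consequence is modest.** A reader might infer that dose escalation or the overall safety conclusion is compromised. The documents do not support that either. Protocol 9.5 plans no formal safety tests. The pausing criteria in protocol 3.2 do not use summarised duration. SAP 4.1 places DSMB reporting outside the SAP. This stands, and it means the gap is one of prespecification, not of inference.

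**Conclusion.** The point holds for the SAP body. Of four primary-endpoint components, three are summarised and one, duration, has neither a derivation nor a place in any of the seven planned AE tables. This is more than missing detail: followed exactly, the enumerated outputs leave a primary component with no summary by dose level, while SAP 3.3 declares no departure from the protocol. It should be corrected, but it changes no estimate, error rate or sample size.

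The conclusion assumes that the unavailable shells and appendices contain no duration summary or duration rule. If they do, what remains is to refer to it in SAP 17.1.

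**What to change.** In SAP 17.1:

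- **Define TEAE duration** from the collected start and stop dates, in hours where times are recorded and otherwise in days with a stated convention. State how partial dates are handled.
- **Add one descriptive table** giving number of events, median, minimum and maximum, by study part and dose level, with placebo shown as in SAP 6.2.
- **Rows:** all TEAEs and treatment-related TEAEs. Add index-knee or injection-site events only if the sponsor defines that group before unblinding, because the SAP's MedDRA-based tabulations define no flare category.
- **Ongoing events:** show them as a separate count and exclude them from the completed-duration statistics, since a plain median, minimum and maximum cannot accommodate censored values.
- **Preferred-term detail:** leave it to the listings.

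If the sponsor intends duration to be listed only, SAP 3.3 should say so, and the sponsor should consider whether the amendment requirement in protocol section 9 applies.

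The cost is one extra table and a short derivation paragraph. No new data collection appears necessary. The table will be sparse in the smallest cohorts, which have 3 active subjects each. The change should be settled before database lock and unblinding, after which SAP 4.3 places the final analyses.

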3. STUDY DESIGN

3.1. **GENERAL DESCRIPTION**

This is a randomized, double-blind, placebo-controlled study to assess the safety, tolerability, pharmacokinetics, and pharmacodynamics of KA34 when administered via intra-articular injection to

CALIBR CBR-KA34-3001 SAP Final 1.0 Document: Author: Version Number: Final 1.0 PPD Version Date: 15MAY2020 Template No: CC

Effective Date: 01Apr2016

subjects with osteoarthritis of the knee. All subjects will receive a 5 mL injection of KA34 or placebo in the affected knee.

The study will consist of approximately 7 cohorts of subjects who will be randomized to receive KA34 or placebo. KA34 will be provided as a solution with a concentration of 200 µg per mL.

KA34 will be administered as a single dose to the following cohorts:

COHORT	DOSE	N PER COHORT
1	50 μg per knee	4 (3 – Active & 1 Placebo)
2	100 μg per knee	4 (3 – Active & 1 Placebo)
3	200 μg per knee	8 (6 – Active & 2 Placebo)
4	400 μg per knee	8 (6 – Active & 2 Placebo)

The decision to escalate to the next dose cohort will be made by the sponsor, based on the recommendation of the Data Safety Monitoring Board (DSMB), following a (blinded) review of all available safety information from Day 8 post-dose of the preceding dose cohort.

Once the safety and tolerability of single doses of KA34 have been assessed, multiple-dose administration of KA34 will be evaluated. The multiple-dose portion of the study will be initiated after a thorough review of the Day 29 safety data from the single-dose cohorts. During the multiple dose portion of the study, KA34 will be administered as 4 weekly doses to the following cohorts:

COHORT	DOSE	N PER COHORT
5	100 μg per knee per injection	12 (9 – Active & 3 Placebo)
6	200 μg per knee per injection	12 (9 – Active & 3 Placebo)
7	400 μg per knee per injection	12 (9 – Active & 3 Placebo)

The doses administered to subsequent cohorts in either the single or multiple dose portions of the study may be lowered if any safety or tolerability issues are identified which suggest that the planned doses may pose a risk to study participants. Additional dose groups may be added to the study depending on the observed safety and tolerability profile of KA34 or if the pharmacokinetic data permit a higher than anticipated dose while remaining within a safe exposure limit based on the toxicokinetics and safety profile from the nonclinical toxicology studies.

The study will be conducted at approximately 4 sites in the United States. Approximately 60 subjects will be randomized to participate in this trial.

3.2. SCHEDULE OF EVENTS

Schedule of events can be found in 'SCHEDULE OF ACTIVITIES' section of the protocol.

Effective Date: 01Apr2016

Copyright © 2017 IQVIA. All Rights Reserved.

3.3. CHANGES TO ANALYSIS FROM PROTOCOL

There are no meaningful changes in the analysis plans relative to the study protocol.

4. PLANNED ANALYSES

4.1. Data Safety Monitoring Board (DSMB)

The decision to escalate to the next dose cohort (single or multiple dose escalation) of the study will be made by the sponsor, based on the recommendation of the DSMB following a (blinded) review of all available safety information from Day 8 post-dose of the preceding dose cohort. The safety information considered during this review will include adverse events, changes in vital sign measurements, clinical laboratory test values, and ECG results. Reporting for the DSMB is to be handled by the data management team and is outside the scope of this document.

4.2. INTERIM ANALYSIS

There are no formal interim analyses planned for this study.

4.3. FINAL ANALYSIS

All final, planned analyses identified in this SAP will be performed by IQVIA Biostatistics and Pharmacokinetics team following sponsor authorization of this Statistical Analysis Plan, database lock and unblinding of treatment.

[figure not shown]
5. ANALYSIS SETS

5.1. ALL SUBJECTS RANDOMIZED SET

The all subjects randomized set will contain all subjects who were randomized to the study treatment.

5.2. SAFETY ANALYSIS SET

The safety analysis set will contain all subjects who receive at least one dose of study medication and will be analyzed according to treatment received. Subjects in this population will be used for all safety,

Copyright © 2017 IQVIA. All Rights Reserved.

dosing and demographic summaries.

5.3. PHARMACOKINETIC ANALYSIS SET

The pharmacokinetic analysis set will consist of all subjects who receive KA34 and have at least 1 measured concentration at a scheduled PK time point after start of dosing without protocol violations or events with potential to affect the pharmacokinetic concentrations. Subjects in this population will be used for all PK parameter analyses.

5.4. PHARMACODYNAMIC ANALYSIS SET

The pharmacodynamic analysis set will consist of all subjects who receive KA34 or placebo (placebo dosed subjects will be pooled and summarized separately) and have at least 1 measured PD value at a scheduled time point after start of dosing without protocol violations or events with potential to affect the PD concentrations. Subjects in this population will be used for all PD analyses/summaries.

6. GENERAL CONSIDERATIONS

Derivation of the PK parameters for KA34 in plasma will be the responsibility of the clinical pharmacokineticist at IQVIA. The PK, PD, and safety summaries, figures and data listings as well as the statistical analysis of the PK and PD variables will be the responsibility of the study biostatistician at IQVIA.

Some minor modifications may be necessary to the planned design of tables, figures, and listings to accommodate data collected during the actual study conduct.

6.1. SUMMARY STATISTICS

For qualitative variables, the population size (N for sample size and n for available data) and the percentage (of available data) for each class of the variable will be presented. Quantitative variables of safety and PD data will be summarized using descriptive statistics, including N, mean, standard deviation (SD), arithmetic coefficient of variation (CV%) as appropriate, median, minimum, and maximum values. Geometric mean and geometric CV% will be included for PK parameter summaries. CV% will not be presented for change from baseline results.

Results will be summarized if n is greater than or equal to 2 per group and otherwise reported as N/A (ie, Not Applicable).

Document: CALIBR_CBR-KA34-3001_SAP_Final 1.0
Author: PPD Version Number: Final 1.0
Version Date: 15MAY2020

Template No: CE Reference: CE

Copyright © 2017 IQVIA. All Rights Reserved.

6.2. Treatment Summarization

For Single Ascending Dose (SAD) and Multiple Ascending Dose (MAD) parts, data will be presented for each dose levels (presented as KA34-XX μ g), with placebo subjects from all dose levels combined into a single, overall placebo group (presented as Placebo). Data for all study subjects combined will also be presented when appropriate.

6.3. PRECISION

Safety variables (ie, clinical laboratory values, vital signs, and ECG intervals), including derivations thereof, will be reported to the same precision as the source data.

All PK concentrations and PD results will be reported and analyzed with the same precision as the source data provided by the bio-analytical laboratory regardless of how many significant figures or decimals the data carry. Derived PK and PD parameters will be rounded for reporting purposes in by-subject listings. The unrounded derived PK and PD parameter data will be considered for the calculation of descriptive statistics and the statistical analysis. For most derived PK and PD parameters, 3 significant digits will be used as the standard rounding procedure, with the following exceptions:

- Parameters directly derived from source data (eg, C_{max}) will be reported and analyzed with the same precision as the source data.
- Parameters derived from actual elapsed sample collection times (eg, T_{max}) will be reported with the same precision as the actual elapsed sampling time value of the source data.

For the reporting of descriptive statistics, the mean, standard deviation, standard error of the mean, and confidence intervals (where appropriate) will be presented to one digit more precision than the source data. The minimum, median, and maximum will be presented to the same precision as the source data. Coefficient of variation will always be reported to 1 decimal place. Coefficient of determination (R²) will be reported to 4 decimal places.

